8.1.1 Definitions

Following are definitions associated with AEs:

Adverse Event - any untoward medical occurrence, unintended disease or injury, or untoward clinical signs (including abnormal laboratory or image findings) in participants, users or other persons, whether or not related to the investigational medical device and whether anticipated or unanticipated (per ISO 14155)

Note: This definition includes events related to the investigational medical device or the comparator. This definition also includes events related to the procedures involved. For users or other persons, this definition is restricted to events related to the use of investigational medical devices.

Clinical Study Protocol – SWELL Study

Serious Adverse Event (SAE) - an adverse event that led to any of the following (per ISO 14155)

- a) death,
- b) serious deterioration in the health of the participant, users or other persons as defined by one or more of the following:
 - 1) a life-threatening illness or injury, or
 - 2) a permanent impairment of a body structure or a body function including chronic disease, or
 - 3) in-patient or prolonged hospitalization, or
 - 4) medical or surgical intervention to prevent life-threatening illness or injury or permanent impairment to a body structure or a body function,
- c) fetal distress, fetal death, or a congenital abnormality, or birth defect including physical or mental impairment.

Note: Planned hospitalization for a pre-existing condition, or a procedure required by the protocol, without serious deterioration in health, is not considered a serious adverse event.

Adverse Device Effect (ADE) – adverse event related to the use of an investigational medical device.

Note: This definition includes adverse events resulting from insufficient or inadequate instructions for use, deployment, implantation, installation, or operation, or any malfunction of the investigational medical device. This definition also includes any event resulting from use error or from intentional misuse of the investigational medical device. This includes comparator if the comparator is a medical device

Serious Adverse Device Effect (SADE) – an adverse device effect that has resulted in any of the consequences characteristic of a serious adverse event (per ISO 14155).

Unanticipated Adverse Device Effect (UADE) - any serious adverse effect on health or safety or any life-threatening problem or death caused by, or associated with, a device, if that effect, problem, or death was not previously identified in nature, severity, or degree of incidence in the investigational plan or application (including a supplementary plan or application), or any other unanticipated serious problem associated with a device that relates to the rights, safety, or welfare of participants (21 CFR 812.3(s)).

Relationship to device and procedure

The potential relationship of the event to the device or procedure will be categorized by the investigator as follows:

Clinical Study Protocol – SWELL Study

- Not related

An adverse event for which sufficient information exists to indicate that there is no causal connection between the event and the device or procedure. The adverse event is due to and readily explained by the participant's underlying disease state or is due to concomitant medication or therapy not related to the use of the device or the procedure. In addition, the adverse event may not follow a reasonable temporal sequence following the procedure.

- Unlikely

The relationship with the use of the device or procedure seems not relevant and/or the adverse event can be reasonably explained by another cause, but additional information may be obtained.

- Possibly related

There is a reasonable possibility that the adverse event may have been primarily caused by the device or procedure. The adverse event has a reasonable temporal relationship to the use of the device or the procedure and follows a known or expected response pattern to the device or procedure, but alternative etiology is equally or more likely compared to the potential relationship to the use of the device or the procedure.

- Probably related

There is a reasonable probability that the adverse event may have been primarily caused by the device or procedure. The adverse event has a reasonable temporal relationship to the use of the device or the procedure and follows a known or expected response pattern to the device or procedure, and an alternative etiology is unlikely or significantly less likely.

- Definitely related

The adverse event has a strong causal relationship to the device or procedure. The adverse event follows a strong temporal relationship to the use of the device or the procedure, follows a known response pattern to the device or procedure, and cannot be reasonably explained by known characteristics of the participant's clinical state or other therapies.

Every effort should be made to determine the cause of each adverse event, because a judgment must be made as to the relationship to the device or procedure. If an investigator cannot assign a causality category the event will be considered possibly related for reporting and analysis.

Clinical Study Protocol – SWELL Study

Note: The occurrence of a diagnostic or elective surgical procedure for a pre-existing condition, unless the condition becomes more severe or increases in frequency, would not be considered procedure- or device-related.

Intensity of adverse events:

- Mild

The adverse event is noticeable to the participant but does not interfere with routine activity.

- Moderate

The adverse event interferes with routine activity but responds to symptomatic therapy or rest.

- Severe

The adverse event significantly limits the participant's ability to perform routine activities despite symptomatic therapy. The adverse event requires medical or surgical treatment or results in hospitalization.

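### All three related grades require a known or expected pattern, so a new kind of serious event with a plausible other cause fits Unlikely and would probably leave the related-SAE proportion

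*Combined protocol and SAP*

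**What the plan says.** Section 8.1.1 has the investigator place each adverse event in one of five causality grades. The three related grades each combine a timing condition with a pattern condition:

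- Possibly related: reasonable timing, and the event "follows a known or expected response pattern to the device or procedure, but alternative etiology is equally or more likely".
- Probably related: reasonable timing, and the event "follows a known or expected response pattern to the device or procedure, and an alternative etiology is unlikely or significantly less likely".
- Definitely related: strong timing, and the event "follows a known response pattern to the device or procedure, and cannot be reasonably explained by known characteristics". Here even an expected pattern is not enough; it must be known.

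Unlikely has no pattern condition. It applies when the relationship "seems not relevant and/or the adverse event can be reasonably explained by another cause, but additional information may be obtained".

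The section then adds a fallback: "If an investigator cannot assign a causality category the event will be considered possibly related for reporting and analysis".

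The same section defines an unanticipated adverse device effect (UADE) as a serious effect caused by or associated with the device that "was not previously identified in nature, severity, or degree of incidence in the investigational plan" or application. Section 8.1.2 lists causality and unexpectedness as separate assessments. Section 7.3 speaks of observing an unexpected serious event that is device-related.

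The Protocol Summary and Section 4.1 make device- and procedure-related SAEs through 3 months a secondary endpoint. Section 7.11 reports their proportion with a 95% confidence interval. None of these places says which grades count as related.

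**The concern.** Whether an event was foreseen and whether the device caused it are different questions. Section 8.1.2 keeps them apart, but the grade definitions build the first into the second. The UADE definition and Section 7.3 both presuppose that an effect nobody foresaw can be attributed to the device. As worded, an effect that is new in nature cannot meet any of the three related grades.

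This matters because the study is single-arm and open-label, so no control group can show up a misattributed event. The investigator grades causality and no adjudication is described. Section 1.0 cites only preliminary studies of radiofrequency at the swell body, so a reaction without a recognised pattern is a realistic possibility. What is at stake is the accuracy of one named secondary safety result.

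**Working it through.** The point turns on wording, so the check is to run four kinds of well-timed serious event through the Section 8.1.1 definitions.

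| Event | Three related grades | Unlikely | Result |
|---|---|---|---|
| A. New kind, plausible other cause | All fail on pattern | Met | Unlikely |
| B. New kind, no other cause | All fail on pattern | Not clearly met; nor is Not related | If left uncategorised, the fallback makes it Possibly related |
| C. Familiar kind, other cause equally or more likely | Possibly met | Also met if that cause is a reasonable explanation | Either grade fits |
| D. Familiar kind, but worse or more frequent than foreseen | Pattern met | Depends on other causes | Can be graded related, and can be a UADE |

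Take A and C with the same competing cause. Possibly tolerates another cause that is equally or more likely; Unlikely needs only a reasonable one. The two grades overlap, and the pattern condition is what removes Possibly from A. The gap is therefore case A.

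**Size for one event.** The plan states no figure for this endpoint. Assume 70 participants in the denominator (Section 7.3) and one SAE whose grade changes. Exact (Clopper-Pearson) 95% limits:

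- Graded Possibly: 1/70 = 1.43%. Lower limit 1 − 0.975^(1/70) = 0.04%; upper limit, the 97.5th percentile of Beta(2, 69), = 7.70%.
- Graded Unlikely: 0/70 = 0%. Upper limit 1 − 0.025^(1/70) = 5.13%.

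**Size over a range.** Section 7.3 gives one nearby figure: 95% confidence of seeing at least one unexpected serious device-related event at an incidence of 2.3%. With n = 70 this gives 1 − (1 − 0.023)^70 = 80.4%; 95% corresponds to an incidence of 1 − 0.05^(1/70) = 4.19%. That mismatch is a separate matter and nothing here rests on it. If a share m of such events were graded Unlikely and not counted, the chance of counting at least one is 1 − (1 − 0.023(1 − m))^70:

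| m (assumed) | 0 | 0.25 | 0.5 | 1 |
|---|---|---|---|---|
| Chance of counting at least one | 80.4% | 70.4% | 55.5% | 0% |

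The documents give no value for m.

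**The case against.** The strongest reply is that the plan already protects against this, and much of that reply stands.

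- **The fallback.** A reader might infer that every new kind of reaction falls out of the endpoint. The documents do not support that. With no competing cause (case B), an event that cannot be categorised is treated as possibly related for reporting and analysis. The fallback does not reach case A, because there a grade is available.
- **Unanticipated effects.** A reader might infer that no UADE can meet the pattern condition. That is wrong: the definition also covers effects unforeseen only in severity or incidence, and those can follow a familiar pattern (case D). Nor does 8.1.1 tie a known or expected pattern to the list of anticipated events in 5.8.1.
- **Septal perforation.** It is missing from the 5.8.1 list, which makes it a tempting example. But Section 7.11 counts it separately with its own interval and no causality condition, so grading cannot remove it from that count.
- **Visibility.** A reader might infer that serious harms would go unseen. Section 8.1.2 requires every SAE to reach the sponsor within 24 hours, and Section 7.14 promises narratives for all SAEs and summaries of seriousness and relationship.
- **Direction.** It would be too strong to say that the grading scheme always errs toward safety. The pattern condition can only remove or downgrade events, but the fallback and the tolerant wording of Possibly push the other way.
- **Investigator latitude.** An investigator could rely on the opening sentence of Possibly, which speaks of a reasonable possibility of causation. That makes misgrading avoidable, but the pattern condition remains in the text.

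**Conclusion.** The concern holds for one class of event: a serious event of a new kind, with reasonable timing and a plausible other cause. By the text it is Unlikely, and it would probably not enter the related-SAE proportion. The word probably is needed because that exclusion is inferred from the grade names.

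The consequence is limited to that proportion. One event moves it between 0/70 and 1/70, with largely overlapping intervals. The endpoint has no hypothesis or threshold, and study success under 5.5.2 rests on the NOSE change alone, so no success decision changes. The illustration assumes a denominator of 70 and one affected event, and the range assumes m; the documents predict neither the number of events nor m.

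The change is still worth making. The grade wording conflicts with the UADE definition, with the separate assessment of unexpectedness in 8.1.2 and with Section 7.3. Whether one related SAE or none is reported could shape how the safety result is read.

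**What to change.** 1. In Section 8.1.1, make a known or expected pattern a supporting consideration rather than a condition in all three related grades.
2. Separate Possibly from Unlikely so that one event cannot fit both. For example, reserve Unlikely for events where another cause is clearly more likely, and change the alternative-cause wording in Possibly to match, so that it covers events where no other cause is clearly more likely. Changing Unlikely alone would leave the overlap.
3. In Section 7.11, state that possible, probable and definite all count as related.
4. In Section 7.11, report all SAEs regardless of causality beside the related-SAE proportion, so that the result does not depend on grading alone.

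The cost is wording in two sections and in the adverse event form instructions; visits, procedures and sample size are unchanged. The downside is that a few more events, some of them coincidental, may be counted as related, and the reported safety rate may look slightly less favourable.

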8.1.2 Documentation and Reporting of Adverse Events

All adverse events will be monitored from the time of study entry through study exit. All adverse events must be reported on the Adverse Event Report eCRF. A description of the event, including onset date, resolution date, action taken, and the outcome should be provided. All adverse events will be followed until they are adequately resolved or reach a chronic, stable state. If a participant reaches the 36-month follow-up visit and is experiencing a new or ongoing adverse event, the sponsor should be contacted to discuss the need and/or methods for continued surveillance of the event. Adverse events will be evaluated by the investigator and differentiated by:

- Seriousness
- Intensity (mild, moderate, severe)
- Causality (in relation to the device or procedure)
- Unexpectedness

Signs and symptoms considered normal postprocedure recovery (eg, postprocedure pain, transient sensory symptoms, fever, postanesthesia symptoms) do not have to be reported as adverse events. If these events require treatment outside that which is considered normal or if the event lasted longer in duration than normal, they should be reported as adverse events.

All adverse events classified as an Unanticipated Adverse Device Effect, Serious Adverse Device Effect, or Serious Adverse Event must be reported to the sponsor within 24 hours of learning of the event.

Sponsor Contact: [name]

[contact]

Email: [contact]

Clinical Study Protocol – SWELL Study

Investigators must also report promptly all unanticipated problems to their IRB/EC and/or regulatory authority involving risks to participants or others and report adverse events according to the local or national reporting requirements. Reporting instructions and contact information will be provided in the site's Regulatory Binder for this study.

8.2 Product Complaints / Device Deficiencies

8.2.1 Definitions

Product Complaint - Any written, electronic or oral communication that alleges deficiencies related to the identity, quality, durability, reliability, safety, effectiveness, or performance of an Aerin product (medical device) after it is released for distribution (per 21 820.3(b)).

Complaint – written, electronic or oral communication that alleges deficiencies related to the identity, quality, durability, reliability, usability, safety or performance of a medical device that has been released from the organization's control or related to a service that affects the performance of such medical device (per ISO 13485).

Reportable Complaint – Any product complaint that represents an event, which must be reported to a regulatory agency including:

- US FDA (per 21 CFR Part 803)
- A Competent Authority within the European Community or a Notified Body (MDD)
- The Canadian HPFB
- Any regulatory agency, within the country of distribution

Device Deficiency – inadequacy of a medical device with respect to its identity, quality, durability, reliability, usability, safety or performance.

Note: Device deficiencies include malfunctions, use errors, and inadequacy in the information supplied by the manufacturer including labeling. This definition includes device deficiencies related to the investigational medical device or the comparator (per ISO 14155).

8.2.2 Documentation and Reporting of Complaints / Device Deficiencies

All product complaints, deficiencies and malfunctions associated with devices will be documented on the appropriate eCRF and/or communicated to the sponsor within 24 hours of first becoming aware of the event.

9.0 Study Administration

This study will be conducted in accordance with elements of ICH E6 Guideline for GCP, Abbreviated Requirements of 21 CFR 812 for nonsignificant risk device studies, the European Standard ISO 14155, the Declaration of Helsinki, the Belmont Report, and any applicable regional or national regulations.

Clinical Study Protocol – SWELL Study

The sponsor has the overall responsibility for the conduct of the study according to all applicable regulatory requirements. The sponsor will have certain direct responsibilities and will delegate other responsibilities to the investigator and study site. The sponsor and investigator will ensure that the study is conducted according to all applicable regulations. All personnel participating in the conduct of this study will be qualified by education and experience to perform their tasks.

The sponsor, treating physician, or any person acting for or on behalf of the sponsor or investigator shall act in accordance the applicable standards, guidelines and regulations.

This study is funded by Aerin Medical. The Clinical Trial Agreement (CTA), mutually signed by the study site and Aerin Medical, describes the agreement between sponsor and site with respect to study financing.

9.1 Investigator Training

Site initiation training will occur prior to the first procedure at a site. Investigators will be trained on the procedure and use of the Vivaer ARC Stylus and Aerin Console. All study staff will be trained, as necessary, to ensure compliance with the protocol and regulatory requirements, as well as to ensure accurate data collection. Site training will include a detailed review of this protocol, use of the EDC system, eCRF completion instructions, adverse event reporting, product handling and inventory, monitoring logistics, and regulatory requirements.

9.2 Study Monitoring

Study monitoring will be carried out in compliance with FDA regulations, ISO 14155, and Good Clinical Practice (GCP) guidelines. The monitoring for this study will be carried out by monitors qualified by experience and training who are Aerin Medical employees or individuals contracted by Aerin to conduct monitoring activities. The study monitors will oversee the conduct of the study either on-site or remotely and evaluate compliance with the protocol, any specific recommendations made by the site's IRB and the signed Investigator Agreement. During the study, phone contacts and site visits will be conducted to ensure protocol compliance. Monitoring will include a verification the informed consent was properly obtained for all study participants, a review of clinical records for accuracy and completeness, resolution of missing or inconsistent results, a review of source documents, and ensuring adverse events, protocol deviations and device usage are properly documented. The monitor will conduct source data verification by verifying eCRFs are consistent with source documents. The investigator will make available to the monitor for review the informed consent forms, source documents, and any other relevant records for all study participants at the site. The investigator and other site personnel will be accessible to the monitor during visits whether on-site or remote and sufficient time is provided to conduct the visits and address questions. If the monitor becomes aware of any deficiencies during the course of the study, the monitor will discuss with the sponsor and investigator to ensure compliance is maintained. A final close-out monitoring visit will occur when the study has been completed or terminated.

9.3 Documentation of Study Findings

9.3.1 Data Management

A secure EDC and management system will be used for entry, storage, review, and management of study data. The system will use the Medrio EDC platform (Medrio, Inc. San Francisco, CA) and be compliant with applicable GCP and regulatory requirements. Investigators are responsible for accurate completion and timely submission of the data collected during the study. Sites will be trained in the use of the system for entering study data and uploading supporting documents and will be given access for this purpose. Data monitoring will be performed to identify missing data, verify data accuracy, and ensure queries are resolved. Any data issues are to be promptly addressed with the investigator. Quality assurance procedures will be established to ensure that complete, accurate and timely data are submitted, protocol requirements are followed, and that complications, adverse events and adverse device effects are correctly reported and investigated as appropriate. The management and retention of these data will be compliant with applicable regulatory requirements.

9.3.2 Case Report Forms

Standardized electronic case report forms (eCRFs) will be used at all participating study sites to collect complete and accurate records of the clinical data. All study data will be entered by study personnel through eCRFs for each participant screened in the study. A unique ID number will be assigned to each participant.

The following eCRFs and logs will be used in this study and submitted at the intervals outlined in Table 1:

- Screening Visit / Study Eligibility (01)
- ICF Checklist (01A)
- Screening Visit – Demographics, Treatment History & Nasal Exam (02)
- CT Settings Checklist (02A) (selected sites only)
- NOSE Scale (03)
- NRS Ease of Breathing– Participant form (04)
- SNOT-22 (05)
- Preprocedure (06A)
- Anesthesia and Procedure (06B)

Clinical Study Protocol – SWELL Study

- Immediate Postprocedure (06C)
- VAS for nasal pain – Participant form (07A)
- VAS for nasal pain – Site form (07B)
- Follow-up Visit (08)
- Participant Satisfaction Survey (09)
- Study Exit (10)
- Device Malfunction Report (11)
- Protocol Deviation (12)
- Adverse Event Report (13A) (reference AE Code List [13B])
- Serious Adverse Event / Unanticipated Adverse Device Effect (SAE / UADE) Report (14)
- Medication Log (15)
- Unscheduled Visit (16)

Clinical Study Protocol – SWELL Study

Table 1. Schedule of case report forms and related materials.

Visit	Visit Window (days)	eCRF	Other
Screening	n/a	01, 01A, 02, 02A*, 03, 04, 05, 15	Informed Consent Nasal assessment images [†] CT imaging*
Study Procedure (preprocedure/anesthesia/treatment)	within 30 days of Screening	06A, 06B,	Nasal assessment images [†] Nasal assessment does not get repeated Preprocedure if the Screening and Treatment visits occur on the same day
Postprocedure	0	06C, 07A, 07B, 15	Nasal assessment images [†]
1-Week (In-office)	+3	07A, 07B, 08, 15	Nasal assessment images [†]
13-Week (In-office)	±14	02A*, 03, 04, 05, 08, 09, 15	Nasal assessment images [†] CT imaging*
6-Month (Remote)	±30	03, 04, 05, 08, 09, 15	
12-Month (Remote)	±30	03, 04, 05, 08, 09, 15	
24-Month (Remote)	±30	03, 04, 05, 08, 09, 15	
36-Month (Remote)	±30	03, 04, 05, 08, 09, 10, 15	
As Needed	n/a	10, 11, 12, 13A, 13B, 14, 16	

[†]Copy de-identified endoscopic video/images collected for study records to USB flash drive and provide to Sponsor.

*Sites selected for substudy only

